9.2 Double-Blind Treatment Period

9.2.1 *Visit 4, Day 15*

As shown in [Table 1](#), the following will be performed at Visit 4:

- Record vital signs
- Conduct brief neurologic examination
- Administer C-SSRS (Since Last Visit version)
- Record concomitant medications
- Review seizure diary
- Perform drug accountability
- Record AEs
- Dispense seizure diary

- Dispense study drug as instructed by IWRS
- Schedule a return to occur in 2 weeks for Visit 5

9.2.2 *Visit 5, Day 29*

As shown in [Table 1](#), the following will be performed at Visit 5:

- Record vital signs
- Measure weight
- Conduct brief neurologic examination
- Administer C-SSRS (Since Last Visit version)
- Record concomitant medications
- Review of seizure diary
- Perform drug accountability
- Record AEs
- Dispense seizure diary
- Dispense study drug as instructed by IWRS
- Schedule a return to occur in 2 weeks for Visit 6

9.2.3 *Visit 6, Day 43*

As shown in [Table 1](#), the following will be performed at Visit 6:

- Record vital signs
- Conduct brief neurologic examination
- Administer C-SSRS (Since Last Visit version)
- Perform 12-lead ECG (standard)
- Draw blood for laboratory safety assessment
- Record concomitant medications
- Review seizure diary
- Perform drug accountability
- Record AEs
- Dispense seizure diary

- Dispense study drug as instructed by IWRS
- Schedule a return to occur in 4 weeks for Visit 7

9.2.4 *Visit 7, Day 71*

As shown in [Table 1](#), the following will be assessed at Visit 7:

- Record vital signs
- Measure weight
- Conduct brief neurologic examination
- Administer C-SSRS (Since Last Visit version)
- Draw blood for YKP3089 levels. Two blood samples will be collected for the determination of YKP3089 plasma levels: the first one will be collected upon subjects' arrival to the study unit; the second one should be collected within 2 to 4 hours after the first blood draw.
- Draw blood for concomitant AED levels
- Record concomitant medications
- Review of seizure diary
- Perform drug accountability
- Record AEs
- Dispense seizure diary
- Dispense study drug as instructed by IWRS.
- Schedule a return to occur in 4 weeks for Visit 8

9.2.5 *Visit 8, Day 99*

As shown in [Table 1](#), the following will be performed at Visit 8:

- Record vital signs
- Conduct brief neurologic exam
- Administer C-SSRS (Since Last Visit version)
- Draw blood for YKP3089 levels. Two blood samples will be collected for the determination of YKP3089 plasma levels: the first one will be collected upon subjects' arrival to the study unit; the second one should be collected within 2 to 4 hours after the first blood draw.

- Draw blood for concomitant AED levels
- Record concomitant medications
- Review seizure diary
- Perform drug accountability
- Record AEs
- Dispense seizure diary
- Dispense study drug as instructed by IWRS.
- Schedule a return to occur in 4 weeks for Visit 9

9.2.6 *Visit 9, Day 127, End of Double-Blind Treatment Period (or Early Termination)*

For subjects who will be entering open-label extension phase, see Section 9.3 for required assessments and procedures.

For subjects who will not be entering the open-label extension phase of the study (after completing the double-blind maintenance or terminating prematurely), the procedures to be followed at Visit 9 are shown in Table 1.

At Visit 9, subjects who discontinue treatment at the end of the double-blind phase of the study will receive study drug for the double-blind study taper (see Section 6.1.2.3) and a new seizure diary. They will be scheduled to return to the clinic for the Follow-up Visit (Visit 10), 14 days after the last dose of study drug, which corresponds to Day 162 after the start of treatment with YKP3089 or placebo.

If participation in the study is being terminated before Visit 9, the subject will undergo at the time of termination all of the evaluations scheduled for Visit 9. If the clinical situation warrants a taper period, subjects will be dispensed study drug for the double-blind study taper (see Section 6.1.2.3). They will be scheduled to return to the clinic for the Follow-up Visit (Visit 10), 14 days after the last dose of study drug (see Table 1 and Section 9.2.7).

As shown in Table 1, the following will be performed at Visit 9:

- Record vital signs
- Measure weight

- Perform full neurologic examination
- Administer C-SSRS (Since Last Visit version)
- Administer Quality of Life in Epilepsy Questionnaire (QOLIE-31-P)
- Administer Clinical Global Impression of Change (CGIC)
- Perform 12-lead ECG (standard)
- Perform urine pregnancy test (for female subjects of child-bearing potential)
- Draw blood for laboratory safety assessment
- Obtain urine for urinalysis
- Record concomitant medications
- Review seizure diary
- Perform drug accountability
- Record AEs
- Dispense seizure diary
- Dispense study drug (taper) as instructed by IWRS
- Schedule a return to occur in 5 weeks for Visit 10

9.2.7 *Visit 10, Day 162 or 14 Days after Last Dose of Study Drug*

Visit 10 represents the Follow-up Visit scheduled for 14 days after the last dose of study drug for subjects who are discontinuing at the end of the double-blind phase of the study and for subjects who discontinue early. There is no Visit 10 for subjects who are entering the open-label phase of the study.

At Visit 10 (or at the Follow-up Visit scheduled for 14 days after the last dose of study drug for subjects who discontinue early), the following will be assessed, as shown in [Table 1](#):

- Record vital signs
- Measure weight
- Perform full physical examination
- Conduct brief neurologic examination
- Administer C-SSRS (Since Last Visit version)
- Serum pregnancy test (for female subjects of child-bearing potential)

- Draw blood for laboratory safety assessment
- Obtain urine for urinalysis
- Record concomitant medications
- Review seizure diary
- Perform drug accountability
- Record AEs

Visit 10 represents the end of study participation for subjects who are discontinuing after the double-blind phase. No study drug will be dispensed at Visit 10. For information about Visits 9 and 11 for subjects who will continue in the open-label extension phase, see Section 9.3.

9.3 Open-Label Extension Phase

The open-label extension phase begins at Visit 9, when the subjects who are to continue in the open-label phase start a blinded study drug conversion period (See Section 9.3.1) instead of the blinded study drug taper that is intended for subjects who are discontinuing after the double-blind treatment period (see 9.2.6).

Visit windows of ± 3 days are allowed for visits 9 and end of study Follow-up Visit, visit windows of ± 2 days are allowed for visits 11 and 12, and visit windows of ± 7 days are allowed for all other open-label visits.

9.3.1 *Visit 9, Day 127: Open-Label Phase*

All subjects who have not discontinued and plan to enter the open-label phase of the study will undergo Visit 9 assessments as shown in Table 2:

- Review and record inclusion/exclusion criteria (the same as for the double-blind phase except for seizure frequency)
- Record vital signs
- Measure weight
- Conduct full physical examination
- Conduct full neurologic examination
- Administer C-SSRS (Since Last Visit version)

- Perform 12-lead ECG
- Perform urine pregnancy test (for female subjects of childbearing potential)
- Draw blood for laboratory safety assessment
- Obtain urine for urinalysis
- Record concomitant medication
- Review seizure diary
- Perform drug accountability
- Review AEs
- Dispense seizure diary
- Dispense study drug (double-blind blister card and open-label bottle) as instructed by IWRS.
- Schedule a return to occur in 2 weeks for Visit 11. Note: There is no Visit 10 for subjects who have not discontinued and who enter the open-label phase of the study.

9.3.2 *Visit 11, Day 141*

The initial target dose for the open-label extension will be 300 mg once daily. The dose of YKP3089 may be reduced to a minimum of 50 mg once daily or increased to a maximum of 400 mg once daily by 100-mg or 50-mg increments.

As shown in [Table 2](#), the following will be assessed at Visit 11:

- Record vital signs
- Conduct brief neurologic examination
- Administer C-SSRS (Since Last Visit version)
- Record concomitant medications
- Perform drug accountability
- Record AEs
- Review seizure diary
- Dispense seizure diary
- Dispense open-label study drug bottles as instructed by IWRS
- Schedule a return to occur in 2 weeks for Visit 12

At this point, the subjects will have finished the blinded conversion from the double-blind regimen and will be using an open-label regimen. Starting at this visit, changes to the subject's concomitant AED regimen are permitted.

9.3.3 *Visit 12: Day 155*

As shown in [Table 2](#), the following will be assessed at Visit 12:

- Record vital signs
- Administer C-SSRS (Since Last Visit version)
- Perform 12-lead ECG
- Perform urine pregnancy test (for female subjects of childbearing potential)
- Draw blood for laboratory safety assessment
- Record concomitant medications
- Perform drug accountability
- Record AEs
- Review seizure diary
- Dispense seizure diary
- Dispense open-label study drug bottles as instructed by IWRS
- Schedule a return to occur in 12 weeks for Visit 13

9.3.4 *Visit 13, Day 239*

As shown in [Table 2](#), the following assessments will be performed at Visit 13:

- Record vital signs
- Measure weight
- Conduct brief neurologic examination
- Administer C-SSRS (Since Last Visit version)
- Record concomitant medications
- Perform drug accountability
- Record AEs
- Review seizure diary

- Dispense seizure diary
- Dispense open-label study drug bottles as instructed by IWRS
- Schedule a return to occur in 12 weeks for Visit 14

9.3.5 *Visit 14, Day 323*

As shown in [Table 2](#), the following assessments will be performed at Visit 14:

- Record vital signs
- Administer C-SSRS (Since Last Visit version)
- Perform urine pregnancy test (for female subjects of childbearing potential)
- Draw blood for laboratory safety assessment
- Obtain urine for urinalysis
- Record concomitant medications
- Perform drug accountability
- Record AEs
- Review seizure diary
- Dispense seizure diary
- Dispense open-label study drug bottles as instructed by IWRS
- Schedule a return to occur in 12 weeks for Visit 15

9.3.6 *Visit 15, Day 407*

As shown in [Table 2](#), the following assessments will be made at Visit 15:

- Record vital signs
- Measure weight
- Conduct brief neurologic examination
- Administer C-SSRS (Since Last Visit version)
- Record concomitant medications
- Perform drug accountability
- Record AEs
- Review seizure diary

- Dispense seizure diary
- Dispense open-label study drug bottles as instructed by IWRS
- Schedule a return to occur in 12 weeks for Visit 16

9.3.7 *Visit 16, Day 491, or Termination from Open-Label Phase—Taper Visit*

As shown in [Table 2](#), the following will be performed at Visit 16 or at the time of early termination from the open-label phase.

At Visit 16, if clinically indicated, the subjects will begin the study drug taper described in Section 6.1.4.3. At the end of this drug taper, the subject will have discontinued YKP3089. The following assessments will be made at Visit 16:

- Record vital signs
- Measure weight
- Conduct full physical examination
- Conduct full neurologic examination
- Administer C-SSRS (Since Last Visit version)
- Perform 12-lead ECG
- Perform urine pregnancy test (for female subjects of childbearing potential)
- Draw blood for laboratory safety assessment
- Obtain urine for urinalysis
- Record concomitant medications
- Perform drug accountability
- Record AEs
- Review seizure diary

For subjects who completed 1 year of open-label treatment:

- Determine whether the subject is benefitting from open-label treatment with YKP3089

For subjects who are benefitting from open-label treatment:

- Dispense open-label medication

- Dispense seizure diary
- Schedule a return to occur in 3 months for next visit
- See section 9.3.9 for further instructions

For subjects leaving the open-label treatment due to any reasons at any time before 1 year or leaving at Visit 16 due to no benefit or any reasons:

- Dispense taper open-label study drug bottles as instructed by IWRS if needed
- Schedule a return to occur in 2 weeks of the last dose for Visit 17 if tapered
- Schedule a return to occur in 2 weeks for Visit 17 if not tapered

9.3.8 ***Visit 17, End of Study Follow-up (14 days from the last dose)***

Visit 17 represents the Follow-up Visit after discontinuation of study drug in the open-label extension phase. This final visit will take place 14 days after the subject's last dose of YKP3089—at any time during the open-label treatment or after 12 months of open-label treatment if there is no additional treatment beyond that point.

As shown in [Table 2](#), the following assessments will be performed at Visit 17:

- Record vital signs
- Measure weight
- Conduct full neurologic examination
- Administer C-SSRS (Since Last Visit version)
- Serum pregnancy test (for female subjects of child-bearing potential)
- Draw blood for laboratory safety assessment
- Obtain urine for urinalysis
- Record concomitant medications
- Perform drug accountability
- Record AEs

No study drug will be dispensed.

9.3.9 *Open-Label Extension Beyond Year One*

Subjects who complete Visit 16 and will continue in the open-label extension beyond year one will adhere to the following visit schedule. The investigator will schedule a return visit in 3 months. Subjects will have study visits every 3 months for a total of 4 visits per study year. The investigator will perform some or all of the following assessments depending up on the visits.

Perform the following every 3 months from Visit 16

- Record vital signs
- Administer C-SSRS (Since Last Visit version)
- Record concomitant medications
- Perform drug accountability
- Record AEs
- Review seizure diary
- Dispense open-label study drug bottles as instructed by IWRS

Perform the following every 6 months from Visit 16

- Measure weight
- Conduct brief neurologic examination
- Perform urine pregnancy test (for female subjects of childbearing potential)
- Draw blood for laboratory safety assessment

Perform the following every 12 months from Visit 16

- Perform full physical exam
- Perform 12-lead ECG
- Obtain urine for urinalysis

This pattern will continue at the discretion of the investigator until development is stopped by SK Life Science Inc, the product is approved for marketing, or anytime at the discretion of SK Life Science Inc.

After the first year of open-label treatment, the visits will be numbered sequentially beginning with Visit 18.

For subjects who discontinue any time after the first year of the open-label treatment, the subject should be brought to the clinic as soon as possible and the investigator will perform the assessments listed under Visit 16. This visit will be assigned the next sequential number. After this visit, the subject will be scheduled to return for Visit 17 (end-of-study follow-up, 14 days after the last dose of study medication).

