10.4 Vital Signs

Vital signs collected in this study are: blood pressure and heart rate (supine for 5 minutes followed by standing for 3 minutes); respiration rate and oral temperature in the supine position. During OLE, these will be collected at Visit 9 (start of OLE), Visits 11, 12, 13, 14, 15, 16, every 3 months after Visit 16, and 14 days after the last dose in OLE.

Weight will only be collected at Visit 9 (start of OLE), Visit 11, 15, 16, every 6 months after Visit 16, and 14 days after the last dose in OLE.

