14 APPENDIX 2: VISIT WINDOWS

14.1 ECG

The following visit windows will be applied for reporting **ECG** results open-label extension results:

Analysis Timepoint	C017 OLE	
	Target Study Day [1]	Window [2]
		Study Days
Baseline	1	<= 1
Start of OLE [3] – Visit 9	127	>= 113 to <= 141
Visit 12	155	>=142 to <= 323
Visit 16	491	>=324 to <=659
Visit 20	827	>=660 to <= 995
Visit 24	1163	>=996 to <=1306
Visit 28	1499	>=1307 to <=1642
Visit 32	1835	>=1643 to <= 2003
Visit 36	2171	>= 2004 to <=2339
Visit 40	2507	>= 2340 to <= 2675
Visit 44 [4]	2843	>=2676

OLE=Open-label Extension

^[1] Relative to the date of the first dose of study drug. For example, Day 1 = the date of the first dose of study drug.

^[2] The study days evaluated for windows of visits during treatment period are on or prior to the last dose day.

^[3] This window should include the study day when the first dose of OLE study medication was given.

^[4] Expected timepoint C017 OLE.

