14.2 Clinical Laboratory Assessments

The following visit windows will be applied for reporting **clinical laboratory** open-label extension results:

Analysis Timepoint	C017 OLE	
I IIII Openii	Target Study Day [1]	Window [2]
		Study Days
Baseline	1	<= 1
Start of OLE [3] – Visit 9	127	>= 113 to <= 141
Visit 12	155	>=142 to <= 239
Visit 14	323	>=240 to <=407
Visit 16	491	>=408 to <= 575
Visit 18	659	>=576 to <=743
Visit 20	827	>=744 to <=911
Visit 22	995	>=912 to <=1079
Visit 24	1163	>= 1080 to <=1247
Visit 26	1331	>= 1248 to <=1415
Visit 28	1499	>=1416 to <=1583
Visit 30	1667	>=1584 to <=1751
Visit 32	1835	>=1752 to <=1919
Visit 34	2003	>=1920 to <=2087
Visit 36	2171	>=2088 to <=2255
Visit 38	2339	>=2256 to <=2423
Visit 40	2507	>=2424 to <=2591

Visit 42	2675	>=2592 to <=2756
Visit 44 [4]	2843	>=2760

OLE=Open-label Extension

- [1] Relative to the date of the first dose of study drug. For example, Day 1 = the date of the first dose of study drug.
- [2] The study days evaluated for windows of visits during treatment period are on or prior to the last dose day.
- [3] This window should include the study day when the first dose of OLE study medication was given.
- [4] Expected timepoint C017 OLE.

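### SAP 14.1 to 14.3 keep a 12-week window grid after Visit 16 although the visits are 3-, 6- and 12-monthly, so later on-schedule safety results fall in late rows and some rows are thinned

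*Protocol*

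**What the plan says.** In the first open-label year visits run on a 12-week cycle. At Visit 15 the site is told "Schedule a return to occur in 12 weeks for Visit 16", and Protocol 9.3.7 fixes the day: "Visit 16, Day 491, or Termination from Open-Label Phase". For subjects who continue, the Visit 16 instruction becomes "Schedule a return to occur in 3 months for next visit", and Protocol 9.3.9 states "Subjects will have study visits every 3 months for a total of 4 visits per study year". The same section puts laboratory tests at 6-month and ECG at 12-month intervals from Visit 16. On tolerance, Protocol 9.3 says "visit windows of ± 7 days are allowed for all other open-label visits".

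The SAP text agrees. SAP 10.4 has vital signs "every 3 months after Visit 16, and 14 days after the last dose in OLE", SAP 10.2 has blood tests 6-monthly after Visit 16, and SAP 10.3 has ECG 12-monthly.

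The windows in SAP section 14 (Appendix 2) do not agree. Their targets after Day 491 step by 84 days for vital signs (14.3), 168 for laboratory tests (14.2) and 336 for ECG (14.1). For example, ECG row Visit 40 covers days ">= 2340 to <= 2675" and laboratory row Visit 28 covers ">=1416 to <=1583". SAP 11.3.2 to 11.3.4 require the summary tables to use these windows.

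On numbering, Protocol 9.3.8 makes Visit 17 the follow-up 14 days after the last dose, and Protocol 9.3.9 numbers the visits after year one from 18. SAP 14.3 has a row called Visit 17 with target Day 575.

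**The concern.** The rows carry visit names, so a reader will take each row as the results of one scheduled visit and its n as the number of subjects assessed then. If the schedule and the grid run at different speeds, subjects who keep the schedule exactly still pass from one row to the next but one. A row in between then loses subjects for a reason unrelated to attrition, and every later row holds results from an earlier scheduled visit than its name says. The laboratory shift tables (SAP 11.3.2) and the QTcF and heart-rate counts (SAP 11.3.3) are presented by visit and inherit both faults.

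The days involved lie within the follow-up that the SAP foresees. Its exposure categories run to 120 months (SAP 8.5), and its diary intervals run past open-label day 3650 (SAP 9). With open label starting at Day 127, that is study day 127 + 3649 = 3776.

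**Working it through.** **Inputs.** Anchor: Day 491 (Protocol 9.3.7). Interval: four visits a year gives 365.25/4 = 91.3125 days. Alternatives are 3 × 30.4 = 91.2 days, from the month used in SAP 8.5, and 13 weeks = 91 days. Windows: as printed in SAP 14.1 to 14.3. Tolerance: ±7 days (Protocol 9.3).

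**The SAP grid reproduces.** 491 + 84×28 = 491 + 168×14 = 491 + 336×7 = 2843, the printed target for Visit 44 in all three tables. An 84-day step is 365.25/84 = 4.35 visits a year, against the protocol's 4. The SAP's own 6-month diary interval is 182 days (SAP 9), against 168 in the laboratory grid.

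**Offset per assessment.**
- Vital signs: 91 − 84 = 7 to 91.3 − 84 = 7.3 days.
- Laboratory: 182 − 168 = 14 to 182.6 − 168 = 14.6 days.
- ECG: 364 − 336 = 28 to 365.25 − 336 = 29.25 days.

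**Where nominal days land.** Day = 491 + step × k, with k the number of the assessment after Visit 16.

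| Series | 91.3-day quarter | Skipped | 91-day quarter | Skipped |
|---|---|---|---|---|
| Vital signs | k=5: 948, row 21; k=6: 1039, row 23 | 22 (954–1037) | k=6: 1037, row 22; k=7: 1128, row 24 | 23 (1038–1121) |
| Vital signs | k=17: 2043, row 34; k=18: 2135, row 36 | 35 (2046–2129) | k=18: 2129, row 35; k=19: 2220, row 37 | 36 (2130–2213) |
| Laboratory | k=5: 1404, row 26; k=6: 1587, row 30 | 28 (1416–1583) | k=6: 1583, row 28; k=7: 1765, row 32 | 30 (1584–1751) |
| ECG | k=5: 2317, row 36; k=6: 2682, row 44 | 40 (2340–2675) | k=6: 2675, row 40 | none |

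The 91.2-day quarter puts the 6th assessments on Days 1038, 1585 and 2680 and skips the same rows as 91.3. Up to the Visit 44 region, the assessments outside the row for their place in the sequence are:
- at 91.3 days, 21 of 26 vital-sign visits, 8 of 13 laboratory samples and 1 of 6 ECGs;
- at 91 days, 20 of 26, 7 of 13 and 0 of 6.

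**With the tolerance.** Assume whole-day deviations, uniform on ±7, around a schedule fixed from Day 491 with a 91.3-day quarter. The 6th laboratory sample is due on Day 1586.75 and reaches row 28 only if it is at least 4 days early: 4 of 15 offsets, or 27%. A simulation of 5,000 subjects gave 26%. If each visit is instead set from the one before, deviations accumulate. The share of continuing subjects with a value in each row was:

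| Row | Fixed from Visit 16 | Set from previous visit |
|---|---|---|
| Vital signs 22 | 49% | 76% |
| Vital signs 35 | 42% | 84% |
| Laboratory 28 | 26% | 63% |
| ECG 40 | 0% | 49% |

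The zero depends on the month length. At 91.2 days the 6th ECG is due on 491 + 364.8×6 = 2679.8, and being 5, 6 or 7 days early (3 of 15 offsets, 20%) brings it into row 40.

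**Labels.** By protocol number the k-th visit after year one is Visit 17 + k. The SAP row meant for it is 16 + k. Laboratory visits are therefore 19, 21, 23 and so on in the protocol, and rows 18, 20, 22 in the SAP. Footnote 2 of SAP 14.3 limits on-treatment windows to days up to the last dose, so its Visit 17 row cannot be the protocol's follow-up visit.

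**The case against.** The strongest reply is that neither document defines 3 months in days for scheduling. At exactly 91 days, rows 22, 35, 28 and 40 are all filled, each on its last day (1037, 2129, 1583, 2675). This stands: which rows are skipped depends on the month length. It does not remove the fault, because the vital-sign and laboratory skips move to the next row. Only an 84-day interval removes them, and no text gives one after Visit 16.

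It also stands that the misses are small (2 to 7 days at 91.3) and within the ±7-day tolerance. A reader might infer that these rows will be empty. The documents do not support that: with the tolerance most are thinned, and if visits are set one from another, as the Visit 16 instruction may be read, the loss is smaller.

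A reader might also infer that results go astray as soon as year one ends, or that long-term safety trends will be wrong. The first five assessments of each type land in their intended rows. Windows assign by actual study day, so a displaced vital sign is still within 42 days of its row target (before the open-ended last row) and the time order holds. The pooling of late ECGs in row 44 comes mainly from that row having no upper limit. Results are also listed by subject, and adverse events, exposure and seizure frequency do not use these windows.

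**Conclusion.** The inconsistency is real. It lies between SAP section 14 and both Protocol 9.3.9 and SAP 10.2 to 10.4; the protocol schedule is not the faulty text. For any quarter of 91 to 91.3 days, on-schedule vital-sign and laboratory results sit one or two rows late from the 6th or 7th assessment after Visit 16 (about Days 1039 to 1128 and 1587 to 1765). Two vital-sign rows and one laboratory row are skipped on nominal days. One ECG row (about Day 2682) is skipped at 91.2 or 91.3 days and none at 91. The shares of thinned rows rest on the assumed pattern of visit deviations.

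The damage is to visit names, row denominators and the by-visit shift and QTcF tables. SAP 11.1 excludes inference for the open-label phase, so no test is touched. This is a modest SAP correction, worth making because the rule as written mislabels visits for subjects who comply fully. The Visit 17 label conflict holds whatever the month length.

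**What to change.** Before open-label database lock, which SAP section 4 allows, re-centre the windows after Visit 16 in SAP 14.1 to 14.3 on the stated 3-, 6- and 12-month schedule. Declare one month length and use it throughout. With the SAP's own 30.4 days, for example, the targets are 491 + 91.2k, 491 + 182.4k and 491 + 364.8k. Set boundaries at the midpoints and make them contiguous. This also clears two slips in the present tables: laboratory days 2757 to 2759 belong to no window, and ECG row widths vary (311 days for 996–1306, 361 for 1643–2003). About (2843 − 491)/91.2 = 26 vital-sign rows then cover the span that now has 28.

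Label the rows by months since Visit 16, or by protocol visit number starting at Visit 18, and keep Visit 17 for the end-of-study follow-up.

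The cost is three revised tables and the matching programming constants. No data collection changes.
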